2.2 Hypotheses

ECM's theory of change is that the program's coaching will enable family physicians and their staff to deliver better care to ECM patients. Patients will increase the use of primary healthcare services, and the care that they receive will be of higher quality. With better management of chronic conditions, patients will have less need for secondary and tertiary services such as (avoidable) inpatient hospital admissions and re-admissions, and ambulatory specialist services, and they will experience better health and higher quality of life.

2.3 Outcomes

Given these hypotheses, we focus on three outcome domains: overall healthcare utilization, provider management of tracer conditions, and measures of PHC-sensitive acute care. In domains one and three, we highlight 3 primary outcomes below; the remaining indicators are all secondary study outcomes.

- 1. *Healthcare utilization*: This outcome will be continuous and measures the following indicators during the intervention year, at the patient level:
 - number of primary health care interactions (**primary outcome**)

- number of inpatient care interactions (hospitalizations) (**primary outcome**)
- number of outpatient (ambulatory) services (**primary outcome**)
- number of inpatient post-hospitalization services (nursing and rehabilitation)
- number of outpatient post-visit services (nursing and rehabilitation)
- number of follow up by telephone
- number of follow ups due to chronic illness

- 2. *Provider management of tracer conditions:* This outcome measures provider compliance with Domain II QBS standards as the measure of quality care provision. The QBS has a set of guidelines for monitoring outlined for managing type 2 diabetes (ICD10 E11), hypertension (ICD10 I12-115) and myocardial infarction (ICD10 I21-I23, I25.2). This outcome measures the share of patients who are managed in compliance with the guidelines for monitoring, out of the total number of patients who have a diagnosis of the three conditions in the intervention year aggregated at the provider level. The guidelines for each condition are described in **Table 1**.

Example outcomes for this domain include:

- For type-2 diabetes: monitoring of glycosylated Hb (HbA1C), creatinine, cholesterol level (1 per year).
- For hypertension high risk patients: monitoring of cholesterol level, cholesterol fractions, glucose/glycosylated Hb, creatinine (1 per year); counselling and appointment with family nurse (per year).
- For myocardial infarction patients: Monitoring of cholesterol level (1 per year), glycosylated Hb (HbA1C) (1 per year), counselling with family nurse (1 per year).

Table 1. QBS Compliance Guidelines

Category	Indicator	Description	Measurement
Diabetes - type II	Monitoring	Glycosylated hemoglobin	1 per year
		Creatinine values	
		Cholesterol values	1 per 3 years
		Cholesterol fraction values	
		Counselling for chronic patient	1 per year
Diabetes - type II	Medication	Prescribed for all diabetes type-II patients	6 prescriptions in 14 months
Hypertension I (low risk)	Monitoring	Glucose or glycosylated hemoglobin	1 per 3 years
		Cholesterol	
		Counselling for chronic patient	1 per year
		Appointment by family nurse	
Hypertension II (moderate risk)	Monitoring	Cholesterol determined for patients under 80 years of age	1 per year
		Cholesterol fractions determined for patients under 80 years of age	
		Glucose or glycosylated hemoglobin	
		Creatinine	
		ECG	1 per 3 years
		Counselling for chronic patient	1 per year
		Appointment by family nurse	
Hypertension III (high risk)	Monitoring	Cholesterol determined for patients under 80 years of age	1 per year
		Cholesterol fractions determined for patients under 80 years of age	
		Glucose or glycosylated hemoglobin	
		Creatinine	
		Counselling for chronic patient	
		Appointment by family nurse	
Hypertension medication 1	Medication	Percentage of active ingredients based prescriptions for hypertension patients (all risk levels)	1 per year
Hypertension medication 2	Medication	Prescriptions for moderate or high-risk hypertension patients	6 prescriptions in 14 months
Myocardial Infarction (MI)	Monitoring	Cholesterol	1 per year
		Glucose or glycosylated hemoglobin	
		Cholesterol fractions	
		Counselling for chronic patient	
Myocardial infarction (MI)	Medication	Prescription of beta-blockers treatment group (incl combination drugs)	6 prescriptions in 14 months
		Prescription of statins treatment group (incl combination drugs)	6 prescriptions in 14 months
Hypothyroidism	Monitoring	TSH (thyroid stimulating hormone) determined	1 per year
Total			

- *3 PHC-sensitive acute care:* We will monitor a set of selected outcomes which capture quality of primary care, following indicators created by the Organization for Economic Co-operation and Development (OECD). Based on the OECD framework, we will construct the following outcomes:
 - Avoidable hospital admissions for asthma, COPD, diabetes, congestive heart failure, and hypertension, defined as the number of hospital admissions with any of the above as primary diagnosis (**Primary outcome**)
 - Emergency department visits (for any condition) (**Primary outcome**)
 - Inpatient readmission within 90 days after any previous inpatient admission (**Primary outcome**)
 - Inadequate follow up care for patients hospitalized for acute inpatient care or surgery: cardiovascular disease, acute myocardial infarction, stroke, hip fracture, cholecystectomy. (This measure is defined as the rate of patients who have follow up from family physician within 90 days of discharge)
 - Incomplete discharge from acute in-patient care (for heart failure, acute myocardial infarction, unstable angina)
 - Share of prescriptions purchased out of all the prescribed medications by provider
 - Incidence of new diagnosis of tracer conditions

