2.3 Patient randomization

The next stage of randomization was conducted at the patient level. From each participating ECM provider, 25 patients were eligible for selection into the ECM program. (This number was based on EHIF's budgetary limitations for the program). Each year, EHIF's algorithm uses their Mini Information System Portal (MISP) to update the list of at-risk patients who have multiple chronic illnesses. For this project, the providers selected in the ECM group evaluated these patients and assigned an additional risk score to each of the patients identified in MISP, as follows:

- 1-Mild/moderate risk of deteriorating health
- 2-Severe risk of deteriorating health

Given the mix of mild/moderate and severe patients within each provider, we conduct a stratified random sampling of patients into ECM based on the risk classification, such that every patient within each risk classification group has equal probability of selection, and there are at most 25 patients selected into the ECM program from each provider. All the patients within every provider are stratified into two strata – one for mild/moderate risk and second for severe risk. From each strata we then randomly selected patients into the treatment proportional to their share in the strata with a maximum of 25 patients selected in treatment. Five providers had identified fewer than 25 patients who had a risk of deteriorating health. For these providers, all the patients were assigned to treatment. The patients assigned to ECM were invited to join ECM by their providers; all patient acceptances and refusals are recorded in their electronic health records which will be shared with the research team during the analysis phase.

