2.4 Statistical model

For outcome (1) and (3), we specify the difference in means in the intervention year using the below specification:

$$Y_{ikt} = \alpha + \beta(ECM_i \times Post_t) + \gamma_1 ECM_i + \gamma_2 Post_t + P_i + \tau_t + \pi_k + (\epsilon_i + \eta_k + \zeta_t)$$

Here, Y_{ikt} is the outcome of patient i , with ECM provider k , at time t . ECM_i is an indicator that the patient is selected into the ECM treatment and $Post_t$ is an indicator that the ECM treatment period has started. Therefore β is the difference-in-difference coefficient of interest. P_i are a vector of patient-level controls, such as prior health care seeking, risk status, or health effects (in various models). τ_t are year fixed effects and π_k are provider controls or fixed effects. Standard errors are clustered with provider-year random effects indicated as $\eta_k + \zeta_t$.

For outcome (2), we specify the difference in means in the intervention year using the below specification:

$$Y_{kt} = \alpha + \beta(ECM_k \times Post_t) + \gamma_1 ECM_k + \gamma_2 Post_t + \tau_t + \pi_k + (\eta_k + \zeta_t)$$

Here, Y_{kt} is the outcome provider k , at time t . ECM_i is an indicator that the provider is selected into the ECM treatment and $Post_t$ is an indicator that the ECM treatment period has started. Therefore β is the difference-in-difference coefficient of interest. τ_t are year fixed effects and π_k are provider controls or fixed effects. Standard errors are clustered with provider-year random effects indicated as $\eta_k + \zeta_t$.

Funding statement

This project received funding from the Georgetown University McCourt School of Public Policy Massive Data Institute, the World Bank's Research Support Board, and the World Bank Strategic Impact Evaluation Fund.

Ethics

This study was approved by Harvard Longwood IRB protocol IRB20-114.

References

1. World Health Organization. Noncommunicable diseases: Progress monitor 2020. (2020).
2. World Bank. The state of health care integration in Estonia (2015).

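### Six primary outcomes, but no stated significance level, family of tests, multiplicity control or rule for claiming an effect

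*Combined protocol and SAP*

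**What the plan says.** Section 2.3 (Outcomes) introduces the primary outcomes with "In domains one and three, we highlight 3 primary outcomes below; the remaining indicators are all secondary study outcomes". Six indicators then carry a primary label:

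- Domain 1 (utilization): primary care interactions, hospitalizations, and outpatient services.
- Domain 3 (PHC-sensitive acute care): avoidable admissions for five named conditions, emergency department visits for any condition, and "Inpatient readmission within 90 days after any previous inpatient admission".

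Section 2.4 (Statistical model) gives one regression form for both domains: "For outcome (1) and (3), we specify the difference in means in the intervention year using the below specification". The difference-in-difference coefficient is the quantity of interest, so there are six primary coefficients. The α in that equation is the intercept, not a significance level.

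Section 2.2 (Hypotheses) predicts directions. Primary care use should rise, and "patients will have less need for secondary and tertiary services such as (avoidable) inpatient hospital admissions and re-admissions". It does not say how many of these predictions must be borne out, or by what test.

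**The concern.** The Background presents the document as a pre-analysis plan, whose purpose is to fix in advance what will count as evidence. Here it is left open whether one significant coefficient out of six is enough to report a primary effect of ECM. If it is, the error rate of that claim is not the per-test level.

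Three of the six outcomes also share events by definition. Avoidable admissions are a diagnosis-based subset of hospital admissions, and a readmission is itself an admission. One chance imbalance in admissions could therefore appear as two or three primary findings that look as if they confirm each other.

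**Working it through.** **Count of primary outcomes.** Three labels in domain 1 plus three in domain 3 give six. Reading the introductory sentence as three in total does not fit the labels; reading it as three per domain does.

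**Inputs.** The plan states no alpha, power or false-positive figure, so there is nothing to reproduce. Assumed: two-sided 0.05 for each test, all six null hypotheses true, and a claim made if any one test is significant. The correlations among the six test statistics are not given, so a range is shown.

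**Independent tests.** Chance of at least one false positive = 1 − (1 − 0.05)^6 = 1 − 0.95^6 = 0.265.

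**Common correlation r.** Six equicorrelated normal statistics with critical value 1.96, by numerical integration (simulation at r = 0.5 also gives 0.207):

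| r | Chance of at least one false positive |
|---|---|
| 0 | 26.5% |
| 0.3 | 24.1% |
| 0.5 | 20.7% |
| 0.7 | 16.4% |
| 0.9 | 10.8% |

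**Overlap among the inpatient outcomes.** Simulation with correlation 0.6 among hospitalizations, avoidable admissions and readmissions, and 0.2 elsewhere, gives 23.6%. With 0.8 among those three it gives 22.0%.

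**Favourable direction only.** Each test then has a 0.025 chance of a false claim: 1 − 0.975^6 = 0.141 if independent. The 0.6/0.2 structure gives about 12.4%, and the 0.8/0.2 structure 11.6%. More primary care use is counted as favourable. Section 2.2 (Hypotheses) does not mention emergency visits, so fewer visits being favourable is an assumption.

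**Other per-test levels, independent.** At 0.01: 1 − 0.99^6 = 0.059. At 0.10: 1 − 0.90^6 = 0.469.

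**One domain alone, unadjusted.** 1 − 0.95^3 = 0.143.

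**With control.** Bonferroni across six, which is also Holm's first step, uses 0.05/6 = 0.0083 per test. That gives 1 − (1 − 0.05/6)^6 = 0.049 under independence and at most 0.05 under any dependence. Control within each domain uses 0.05/3 = 0.0167 at the first step. The chance of any false positive over both domains is then 1 − (1 − 0.05/3)^6 = 0.096 if independent, and at most 0.05 + 0.05 = 0.10.

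**The case against.** The strongest reply is that the percentage describes a rule the plan never adopts. Nothing says that a single significant coefficient establishes that ECM works. If the six results are reported as six separate, pre-named estimates, each keeps its own per-test error rate. If all six had to succeed, there would be no inflation at all. This stands as a limit on the figure, which illustrates one permitted reading. It does not answer the omission, because no reading is written down.

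A second reply is that the family of six is only one choice. The outcomes are grouped by domain and the predictions differ, so inference by domain is reasonable. The unadjusted figure is then 14.3% per domain. This also stands, but a domain-wise family has to be declared too, and 14.3% is still well above 5%.

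Third, the predicted directions and the overlap among inpatient outcomes lower the rate. They do, to about 12% to 14% for favourable results only, or 10.8% at a common correlation of 0.9. Either is still more than twice the assumed level.

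Finally, readers could compute adjusted p-values later from the six reported results. That is true of the p-values. It cannot restore a claim rule chosen before the results were seen.

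**Conclusion.** The concern holds. The established defect is that the plan names six primary outcomes without an alpha, a family of tests, an adjustment, a hierarchy or a claim rule. Its size depends on the assumed 0.05 level, on all six nulls being true and on claiming any one result. Under those assumptions the false-positive chance is about 21% to 26% for common correlations from 0.5 down to 0, and lower if correlations are higher.

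The plan should be changed, but the design is not undermined. The primary outcomes are named and separated from the secondary ones, and the six estimates remain usable. What is undefined is the meaning of a primary claim.

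**What to change.** In section 2.3 (Outcomes), say that there are three primary outcomes in each of domains one and three, six in total. In section 2.4 (Statistical model), state the alpha and sidedness, the family of tests and the rule for claiming a primary effect.

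A sound default is to report Holm-adjusted p-values across the six beside the unadjusted estimates and confidence intervals, and to base any primary claim on the adjusted values. Holm is valid under any dependence, so the unknown correlations do not matter.

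Two alternatives are acceptable if stated in advance:

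- **Holm within each domain**, if separate claims per domain are intended, with the chance of any false positive over both domains (up to about 10%) disclosed.
- **Step-down p-values from re-randomising patients within provider and risk stratum**, which use the overlap among outcomes to regain power. This suits the comparison of patients within ECM providers. Section 2.3 (Patient randomization) says of five providers with fewer than 25 at-risk patients: "For these providers, all the patients were assigned to treatment". Their assignment cannot be redrawn, so they add nothing to the re-randomisation, and the plan should say how they are handled in the estimate.

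The cost is two or three sentences and a few lines of code, with no new data. The price is a stricter threshold for each single outcome: at an assumed 0.05, the smallest p-value must fall below 0.0083 across six, or below 0.0167 within a domain of three.

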2.1.1 EHIF billing data

For all the data on the outcomes such as health care utilization, provider management of tracer conditions and markers of quality of care we use longitudinal digitized billing records. This data includes every health system interaction for Estonian citizens covered by EHIF. We have electronic billing records spread over eight health care services categories - primary health care, day care, outpatient care, outpatient nursing care, outpatient rehabilitation care, inpatient care, inpatient nursing care, and inpatient rehabilitation care over a 10 year period (2009 until 2019). Each dataset contains three elements. First, every care type contains a claims summary dataset, identified by a bill number. These are initiated by the provider after every episode of care. This data includes the duration of a treatment, type of care, and physician and patient details in reference to the care episode. Second, claims summary dataset is accompanied by a diagnosis dataset that describes all the diagnosis which were relevant to the given care episode. Finally, the third accompanying dataset is the procedures dataset that describes all the medical procedures that were conducted within a given episode of care. We have the billing record containing the associated single insurance payer insurance fund claims, the diagnosis and treatment for each claim filed. In each of these claims we use the International Classification of Disease (ICD) codes of diagnoses, and the procedures.

All the key outcomes of this study will utilize these systems of data, de-identified in compliance with Health Insurance Portability and Accountability Act (HIPAA) regulations.

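### First diagnoses of tracer conditions are put through the ECM x Post difference-in-difference model, where the pre-period adds variance to the estimate and removes none

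*Combined protocol and SAP*

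**What the plan says.** Section 2.3 Outcomes lists "Incidence of new diagnosis of tracer conditions" as the last item of domain 3. It is not marked primary, and the same section states that "the remaining indicators are all secondary study outcomes". No look-back, washout, risk set or rule for patients already diagnosed is given. Domain 2 names the tracer conditions as type 2 diabetes, hypertension and myocardial infarction.

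Section 2.4 Statistical model opens with "For outcome (1) and (3), we specify the difference in means in the intervention year using the below specification". The equation that follows is a patient-level panel model with ECM, Post, their product, year effects, patient controls and provider terms. ECM "is an indicator that the patient is selected into the ECM treatment", and the coefficient on the product "is the difference-in-difference coefficient of interest". No domain 3 outcome is exempted.

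Section 2.1.1 EHIF billing data describes claims "over a 10 year period (2009 until 2019". Section 2.3 Patient randomization says that patients came from an algorithm run each year to "update the list of at-risk patients who have multiple chronic illnesses".

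**The concern.** In a randomised comparison, subtracting a pre-period difference pays off only if the pre-period outcome is positively and fairly strongly correlated with the post-period outcome. Visit counts may meet that condition. A first diagnosis of a chronic condition does not: a patient who had the event before ECM cannot have it afterwards, and a patient still at risk afterwards had no event before. The pre-period term then brings its own sampling error and removes none.

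At stake is the precision of one secondary outcome. If diagnosed patients remain in the denominator, how the estimate reacts to a chance imbalance in baseline prevalence is also affected.

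**Working it through.** **No plan figure to reproduce.** The documents give no event rate, SD, effect size or power for this outcome. From the abstract: 2,389 patients selected and 6,739 - 2,389 = 4,350 not selected, so f = 1/2,389 + 1/4,350 = 0.000648.

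**Assumptions, not in the documents.** Worked example: one condition, 30% already diagnosed when claims open, 3% yearly incidence, no ECM effect. Existing cases first appear in 2009, there are 11 pre-years (2009-2019), and the ECM year comes next.

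**Post-only comparison.** Share still at risk in the ECM year: 0.70 x 0.97^11 = 0.501. SE among those at risk = sqrt(0.03 x 0.97 / 0.501 x f) = 0.0061.

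**One pre-year (2019).**
- Diagnosed patients removed: the pre and post differences are uncorrelated, and Var(pre)/Var(post) = 0.97, the ratio of the two risk sets. SE ratio = sqrt(1 + 0.97) = 1.404.
- Diagnosed patients kept, coded 0: let p and q be the per-patient event probabilities before and after. The events exclude each other, so their covariance is -pq. SE ratio = sqrt{[q(1-q) + p(1-p) + 2pq] / [q(1-q)]}. With p = 0.0155 and q = 0.0150 this is 1.436. With p = q = 0.05 it is sqrt(0.100/0.0475) = 1.45.

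**Eleven pre-years.**
- Coded 0: the probability of a pre-period event is Q = 1 - 0.501 = 0.499. Variance terms: Q(1-Q)/121 = 0.00207; q(1-q) = 0.01479; 2Qq/11 = 0.00136. SE ratio = sqrt(0.01822/0.01479) = 1.110.
- Removed, with year effects: Var(pre) is proportional to the sum of R p(1-p) over the squared sum of R, where R is each year's share at risk and p that year's event rate. This is 0.391/6.943^2 = 0.0081, against 0.0291/0.501 = 0.0581 for post. SE ratio = sqrt(1 + 0.0081/0.0581) = 1.067.

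SE of the difference-in-difference estimate divided by the SE of the post-only comparison:

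| Pre-years | Example, coded 0 | Example, removed | Three-condition simulation, coded 0 |
|---|---|---|---|
| 2009-2019 | 1.110 | 1.067 | 1.07-1.11 |
| 2011-2019 | 1.071 | 1.046 | 1.05-1.09 |
| One year only | 1.436 | 1.404 | 1.39-1.47 |

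The simulation assumed 2009 prevalence of hypertension 20-50%, diabetes 8-20% and MI 2-6%, yearly hazards of 4-8%, 2-3% and 0.8-1.5%, and existing cases first seen in 2009 (80%) or 2010 (20%).

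**Wider range.** For 10-70% already diagnosed and 1-5% incidence, 11 pre-years give 1.08-1.32 (coded 0) or 1.04-1.20 (removed with year effects). One pre-year gives 1.40-1.45 throughout.

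**Could positive correlation rescue it?** Subtraction helps only if the correlation exceeds half of SD(pre)/SD(post): about 0.5 with one pre-year, and 0.5 x sqrt(0.0081/0.0581) = 0.19 in the 11-year example. Simulated correlations were 0 to 0.06 with patients removed, including shared frailty and selection on multimorbidity, and -0.10 to -0.16 with 0-coding.

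**Bias.** With no ECM effect the mean estimate was within 0.0004 of zero in every scenario, which is simulation error.

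**Look-back.** Apparent 2009 incidence is 0.30 + 0.70 x 0.03 = 32%, against 3% later. Dropping 2009-2010 lowers the SE by 0-3% in the three-condition simulation and by 2-4% in the example. The effect is larger only where many are already diagnosed and incidence is low (70% and 1%, coded 0: 1.32 falls to 1.06).

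**Chance imbalance, 0-coding only.** Take 2 points more prevalence in one arm and a 6% hazard. Post-only error: -0.06 x 2 = -0.12 points. The 11-year pre-mean differs by 2/11 = 0.18 points, so the difference-in-difference error is -0.30 points. The extra 0.18 is a third of one SE (about 0.54 points). A 2-point imbalance is itself about 1.6 SE even at 50% prevalence, where the SE is sqrt(0.25 x f) = 1.27 points.

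**The case against.** Four objections carry weight.

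- **It is one secondary outcome and the estimate is unbiased.** Both are true. No primary result depends on this.
- **The cost is the general price of differencing a weakly autocorrelated outcome.** It is, but here the correlation is zero or negative by construction, so no choice of pre-years turns it into a gain. Patient controls and provider effects do not help either: in a balanced panel the interaction, net of its main effects, is orthogonal to every covariate that does not change over time. Adding baseline diagnosis status and provider dummies to the model left the coefficient unchanged.
- **The lead-in to the model speaks of the intervention year.** The equation and the named coefficient are pre/post. If an intervention-year comparison is meant, the plan should say so for this outcome.
- **Incidence ordinarily implies an at-risk denominator.** That is a fair reading, and under it the worsened-imbalance argument falls away. The loss of precision remains.

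A reader might go further and infer that the growing look-back is the main cause, or that it biases the result. The documents do not support this. Year effects absorb the shift common to both arms, patients were randomised within provider, and the later pre-years hold genuine incidence. A reader might also set the steep apparent fall after 2009 beside the 40-45% penalty. These belong to different choices: the fall needs the earliest years in the model, while the large penalty needs a single pre-year, and if that year is 2019 it already has ten years of look-back. The documents do not state the pre-years, the ECM start date, the denominator or any plan to report pre-period trends.

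**Conclusion.** The concern holds as a loss of precision. As specified, the pre-period term makes the estimate for first diagnoses noisier than a plain intervention-year comparison in every scenario computed, and does not bias it. The size is about 5-11% of the SE with many pre-years under mid-range assumptions, and about 40-45% with one. With all 11 years it could reach 20-32% if most patients were already diagnosed when claims opened and incidence was low. All rates are assumed, as is an ECM year directly after 2019.

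The worsening of a chance prevalence imbalance applies only if diagnosed patients are kept and coded 0, and it is modest. Early look-back is a secondary issue, and it arises only if the earliest years enter the model. For myocardial infarction the argument also requires that a repeat event does not count as new, which the plan leaves open.

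**What to change.** Take this outcome out of the ECM x Post model and state the following in section 2.4 Statistical model:

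- For each tracer condition separately, the risk set is patients with no claim for that condition before ECM start, with the same look-back for everyone: either all available claims or one fixed window. A short window would count as new some patients with older claims, so the choice should be made and justified in advance.
- State whether a repeat infarction counts as new.
- Compare selected with unselected patients on first diagnosis in the intervention year only, adjusting for provider and risk class, with no pre-period term.

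This is a free improvement: SAP wording and one extra data step, with no data beyond the claims already planned. Where the event is a true first diagnosis, the patients left out of a risk set cannot have it, so nothing is lost by excluding them. The five providers whose patients were all assigned to ECM add nothing to a within-provider contrast. With fewer than 25 patients each, that is at most 5 x 24 = 120 of 6,739.
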